## STUDY DESIGN

As in previous randomized controlled trials executed by our research group, the AHSQC will serve as a platform for data collection. Additional data not captured by the AHSQC will be recorded by a trained study coordinator or research fellow and uploaded into Research Electronic Data Capture ( RedCAP®). Baseline and intraoperative variables, as well as some of our outcomes of interest (30-day pain scores, hospital length of stay, PRQOL), are already captured within the AHSQC database, allowing for follow-up and data capture with minimal additional effort outside that of routine care (11).

This will be a double-blind, 3-arm, randomized controlled trial with a treatment 1: treatment 2: control allocation ratio of 1:1:1. No important changes to the methods after trial commencement are anticipated. We anticipate that this will be a single-institutional study of patients undergoing elective open ventral hernia repair at Cleveland Clinic Comprehensive

Hernia Center ( Main Campus, Cleveland Clinic Foundation, Cleveland, Ohio, USA) performed by 4 staff surgeons: [name] (PI), [name] (co-I), [name] (co-I) and [name] (co-I). Nonetheless, we do not discard to turn this trial into a multi-institutional trial in the future. No important changes to the methods after trial commencement are anticipated. No interim analyses will be performed, and no stopping guidelines are needed since the interventional arms of this study are already currently performed at our institution, and we do not anticipate adverse events requiring study suspension.

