Inclusion criteria are all adult patients (at least 18 years of age) undergoing open, elective, clean or clean-contaminated (wound classification), ventral hernia repairs with mesh placed in retromuscular position. We have no restrictions on hernia size, and the indication of the operation will be at the discretion of the attending surgeon. Exclusion criteria include: (1) patients unable to give informed consent, (2) patients with allergy, hypersensitivity or contraindication to bupivacaine, (3) patients with history of chronic liver disease with moderate or severe impairment in liver function defined as a Child-Pugh class B or C (4) patients with a history of chronic renal insufficiency on dialysis; (5) patients who are considered chronic opioid users, defined as daily or near daily use of opioids for at least 90 days in the past year and (6) patients from vulnerable populations as further detailed in this protocol. Patients scheduled for minimally invasive hernia repairs or open ventral hernia repairs with mesh placed in a position other than retromuscular will also be considered exclusion criteria. Also, open repairs performed through a different incision than the standard midline approach will also be considered exclusion criteria.

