## OUTCOMES OF INTEREST

### **Primary outcomes of Interest**

Primary outcomes of interest are opioid requirements and pain scores over initial 72 hours of the postoperative period. Opioid requirements will be assessed by measuring the cumulative dose of opioids administered intravenously (infused through a patient-controlled analgesia device as well as the quantity of opioids administered intravenously as rescue, if needed) and the quantity of opioids administered through oral preparations. This will be assessed at time points: at day of surgery (while patients are at PACU or the nursing floor), at postoperative days 1, 2 and 3. Additional time points include daily assessments during the rest of the hospital stay up to a maximum of 7 days. The total dose of opioids used at each time point will be recorded and converted into morphine equivalents for standardization and analysis. We will record the cumulative dose of opioids from 0 hours to 72 hours after the operation and for the total hospital length of stay (up to a maximum of 7 days). In addition, we aim to record the dose of opioids administered intra-operatively by the anesthesiologist, time for first oral opioid dose over the first 72 hours (discontinuation of PCA), and the percentage of patients not requiring opioids over the first 72 hours.

Pain scores will be determined using a 100mm visual analog scale (VAS). The VAS is a 100mm horizontal line with two endpoints: 0 (no pain) and 100 (worst imaginable pain). While in the hospital, subjects are to assess, “How much pain are you experiencing right now?” Pain scores will be assessed at baseline during preoperative evaluation, at day of surgery (PACU or nursing floor), at postoperative days 1, 2 and 3. Additional time points include daily assessments during the rest of the hospital stay up to a maximum of 7 days.

Additional pain scores will be obtained using the Patient-Reported Outcome Measurement Information System (PROMIS) Pain Intensity 3a survey, which is part of the

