**Randomization**

Patients will be randomized using a computer-generated random allocation sequence, by the investigational pharmacy personnel. The random allocation sequence will be implemented with REDCap®, where a randomization allocation table will be generated and uploaded into REDCap® by the study statistician listed in this protocol. Randomization will occur during the operation at the end of adhesiolysis, and at the beginning of abdominal wall reconstruction, to allow for sufficient time for the investigational pharmacy to prepare and dispense the assigned intervention. This study will be double-blinded since patients will be blinded to their assigned intervention until their participation in the study is complete, and also surgeons will be blinded to the intervention assigned to the subject. Only the investigational pharmacy will be aware of the

assigned intervention and this information will be stored in the appropriate randomization platform in REDCap. The study coordinator and other research personnel who will be abstracting opioids doses and pain scores from patients will also be blinded to the intervention that was assigned to patients.

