## STATISTICAL ANALYSIS

Statistical analysis will be performed by the DDSI statistician listed in this protocol, who will determine the appropriate statistical tests for each outcome of interest. Categorical variables will be reported using proportions and analyzed using Pearson's Chi-square. Continuous variables will be reported using median and interquartile range due to their non-parametric nature and examined using either a Student's t-test or a Wilcoxon signed rank test. Pain scores,

opioid requirements, hospital length of stay, and PRQOL requirements will be compared using Mann-Whitney U tests.

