#### PLAN FOR OBTAINING INFORMED CONSENT

Screening for eligible subjects will be performed in clinic, by the participating surgeon (PI or Co-is), during preoperative evaluation. For each subject, written informed consent will be obtained before any protocol-related activities. As part of the informed consent procedure, the principal investigator, surgeon co-investigator, or one of the approved study coordinators will explain verbally and in writing the nature, duration, and purpose of the study in such a manner that the subject is aware of potential risks, inconveniences, or adverse effects that may occur. Subjects will be informed that they may withdraw from the study at any time and will receive all information required by federal regulations.

Following identification of a potential study participant, the investigator or the study coordinator will be responsible for instituting the informed consent process in a face-to-face manner. Before starting any study procedures, the investigator will discuss the proposed research study in detail with the potential subject during the office visit to discuss treatment options. The subject will be allowed ample time to read and review the informed consent document and ask questions. The informed consent document will be reviewed with the subject in depth by the participating investigator or designated member of the research team to ensure that the potential participant has a thorough understanding of the study protocol and understands the potential risks and benefits of study participation and his or her rights as a study participant. The investigators will be available by phone or office visit to answer any questions that the participant may have.

After consideration, the subject may return if necessary for another visit with the investigator and ask additional questions before signing the informed consent document to participate in this study.

After the subject has read and reviewed the informed consent document and has agreed to participate, he/she will be asked to sign and date the document. The study member obtaining consent will also sign and date the form, and documentation of the informed consent process will be included in the research file (i.e., the person who obtained consent, where and when consent was obtained, and who was present during the process). A copy of the consent form will be given to the subject for their records.

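### Sub-threshold preoperative opioid use is eligible but is neither named as a recorded variable nor used in the primary opioid comparison; adjusting for it would be a cheap gain in precision

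*Combined protocol and SAP*

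**What the plan says.** STUDY DESIGN excludes chronic opioid users, defined by "daily or near daily use of opioids for at least 90 days in the past year". No other criterion limits prior opioid use, so intermittent or shorter use is eligible.

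Eligibility is settled before surgery. PLAN FOR OBTAINING INFORMED CONSENT states: "Screening for eligible subjects will be performed in clinic, by the participating surgeon (PI or Co-is), during preoperative evaluation". Randomisation comes later, during the operation. On what is recorded, STUDY DESIGN says "Baseline and intraoperative variables, as well as some of our outcomes of interest (30-day pain scores, hospital length of stay, PRQOL), are already captured" in the registry, with other data going to REDCap. Prior opioid use is not named in either place.

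The Randomization section says "Patients will be randomized using a computer-generated random allocation sequence, by the investigational pharmacy personnel" and names no stratification factor; the allocation is a "treatment 1: treatment 2: control allocation ratio of 1:1:1".

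Under Primary outcomes of Interest: "Primary outcomes of interest are opioid requirements and pain scores over initial 72 hours of the postoperative period". STATISTICAL ANALYSIS then says that "opioid requirements, hospital length of stay, and PRQOL requirements will be compared using Mann-Whitney U tests". It leaves room for choice by the statistician, "who will determine the appropriate statistical tests for each outcome of interest", but no covariate, regression model or stratified test appears anywhere.

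**The concern.** How much opioid a patient takes after surgery plausibly depends on how much the patient was taking before it. The plan treats prior exposure as important enough to exclude its extreme form, then makes no use of the variation that remains. If that variation is prognostic, two things follow. The unadjusted comparison carries outcome variance that could have been removed at no cost in patients. And if one arm happens to receive more prior users than another, the observed difference in opioid dose moves with that imbalance and the planned analysis does not correct for it. The trial is sized at 80% power with no stated margin, so even a few points are worth having.

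**Working it through.** **Inputs from POWER CALCULATION.** A 30% reduction against placebo, alpha 0.05 (sidedness not stated; two-sided assumed), 80% power, 49 per arm, 10% dropout, 54 per arm, 162 in total.

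**The plan's own figure.** No mean or standard deviation is given, so 49 per arm cannot be reproduced directly; it can only be back-solved.
- For a two-sample t-test, power depends on d × √(n/2), where d is the difference divided by the SD. Power of 80% at n = 49 needs d = 0.572.
- With a difference of 0.30 of the control mean, the coefficient of variation is 0.30 / 0.572 = 0.52. (The normal approximation gives d = 0.566 and 0.53.)
- Dropout: 49 × 1.1 = 53.9, so 54; 3 × 54 = 162. Evaluable patients after 10% loss: 54 × 0.9 = 48.6 per arm.

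The sample-size text refers to opioids over the whole stay. I assume that the same standardised effect applies at 72 hours.

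**Gain from covariate adjustment.** If prior use explains a share R² of the outcome variance, the residual SD is SD × √(1 − R²), and d becomes d / √(1 − R²). R² is assumed.

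| R² | Power at 48.6 per arm | Equivalent unadjusted n per arm, 48.6 / (1 − R²) |
|---|---|---|
| 0 | 79.7% | 48.6 |
| 5% | 81.7% | 51 |
| 10% | 83.7% | 54 |
| 20% | 87.7% | 61 |

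In terms of correlation, 0.2 (R² = 4%) moves 80.0% to 81.6% at 49 per arm, and 0.3 (R² = 9%) moves it to 83.6%.

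**Gain from a stratified rank test.** The table applies to an adjusted comparison of means. Simulating a van Elteren test with two strata at 25% prevalence, against the unadjusted Mann-Whitney, gives changes in power of about −1, +1, +3 and +7 points at R² of 0, 5%, 10% and 20%. These are approximate, to within about a point.

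**Chance imbalance.** Assume that a proportion p = 25% are sub-threshold users, with 54 per arm.
- SE of the difference in proportions between two arms = √(2 × 0.25 × 0.75 / 54) = 0.083.
- Probability of a gap of 10 points or more, in either direction: 23% by the normal approximation, 22% exactly.

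**Effect of a 10-point gap on the mean.** Let s be the user-minus-non-user difference as a fraction of the overall control mean. Then R² = s² × p(1 − p) / CV², so s = CV × √R² / √(p(1 − p)), with √(0.25 × 0.75) = 0.433. The dose ratio of users to non-users is 1 + s / (1 − 0.25s).

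| R² | s | Dose ratio | Shift from a 10-point gap (0.10 × s) |
|---|---|---|---|
| 5% | 0.27 | 1.3 | 2.7% |
| 10% | 0.38 | 1.4 | 3.8% |
| 20% | 0.54 | 1.6 | 5.4% |

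The hypothesised effect is 30%.

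**The case against.** The strongest reply is that nothing here is wrong. Randomisation makes the unadjusted Mann-Whitney test valid, its error rate already allows for chance imbalance, and any unadjusted randomised comparison could be described in the same way. That stands. A reader might infer bias or an inflated type I error; the documents support neither.

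A reader might also infer that a none/any classification is already in hand because the exclusion has to be applied. That goes too far. Applying it needs only a yes or no against the 90-day threshold, and no section says that the answer is recorded. The history asked at screening could be extended and recorded, but this has to be arranged.

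The gain may also be small. Excluding chronic users removes the part of the range where prior use should predict most, and a none/any split places a brief course months earlier alongside near-threshold use. At a correlation of 0.2 or less the gain is under 2 points of power. This stands too, and it is why the size is stated conditionally.

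It is tempting to illustrate the imbalance with users needing twice the dose, which gives a shift of 0.10 / 1.25 = 8%. That is not consistent with the power figures: at 25% prevalence a twofold ratio implies R² = 0.1875 / (0.524 × 1.25)² = about 44%, far above the 5–20% range.

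Other predictors are available, notably the baseline VAS score, which the plan does collect. The documents do not show that prior opioid use is the better covariate, and nothing prevents using both.

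Finally, the statistician's freedom to choose tests does not answer the point. An adjustment chosen after an imbalance has been seen carries much less weight than one fixed in advance.

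**Conclusion.** This is a cheap improvement, not an error. Sub-threshold users are eligible, their prior use is not named as recorded, and neither the randomisation nor the primary opioid comparison uses it. The cost is lost efficiency and exposure to chance imbalance.

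The likely benefit is modest: about 2 to 8 points of power with a covariate-adjusted comparison if prior use explains 5% to 20% of the variance, less with a two-stratum rank test, and nothing or a slight loss if it is not prognostic. A 10-point imbalance between two arms, expected in about 22–23% of trials at 25% prevalence, would move the mean by roughly 3% to 5% against a 30% target.

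All of this rests on an assumed prevalence and R², a two-sided test, and an SD inferred from the stated sample size.

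**What to change.** Add one field to REDCap, completed at screening and before randomisation: preoperative opioid use in the past year, none / any below the exclusion threshold.

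In STATISTICAL ANALYSIS, pre-specify that the 72-hour opioid comparison uses one of the following, chosen before unblinding:
- a covariate-adjusted model on ranked or log-transformed morphine equivalents, with prior use as a covariate. If the log scale is used, state how zero doses are handled, since the plan expects to report patients who need no opioids in that period;
- a van Elteren test stratified by prior use.

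Keep the unadjusted Mann-Whitney test as a sensitivity analysis. Eligibility, treatment and sample size do not change.

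The cost is one extra field, a sentence or two of analysis text and a slightly more complex primary analysis. With van Elteren there is also a loss of about 1 point of power if prior use turns out not to be prognostic.

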## OUTCOMES OF INTEREST

### **Primary outcomes of Interest**

Primary outcomes of interest are opioid requirements and pain scores over initial 72 hours of the postoperative period. Opioid requirements will be assessed by measuring the cumulative dose of opioids administered intravenously (infused through a patient-controlled analgesia device as well as the quantity of opioids administered intravenously as rescue, if needed) and the quantity of opioids administered through oral preparations. This will be assessed at time points: at day of surgery (while patients are at PACU or the nursing floor), at postoperative days 1, 2 and 3. Additional time points include daily assessments during the rest of the hospital stay up to a maximum of 7 days. The total dose of opioids used at each time point will be recorded and converted into morphine equivalents for standardization and analysis. We will record the cumulative dose of opioids from 0 hours to 72 hours after the operation and for the total hospital length of stay (up to a maximum of 7 days). In addition, we aim to record the dose of opioids administered intra-operatively by the anesthesiologist, time for first oral opioid dose over the first 72 hours (discontinuation of PCA), and the percentage of patients not requiring opioids over the first 72 hours.

Pain scores will be determined using a 100mm visual analog scale (VAS). The VAS is a 100mm horizontal line with two endpoints: 0 (no pain) and 100 (worst imaginable pain). While in the hospital, subjects are to assess, “How much pain are you experiencing right now?” Pain scores will be assessed at baseline during preoperative evaluation, at day of surgery (PACU or nursing floor), at postoperative days 1, 2 and 3. Additional time points include daily assessments during the rest of the hospital stay up to a maximum of 7 days.

Additional pain scores will be obtained using the Patient-Reported Outcome Measurement Information System (PROMIS) Pain Intensity 3a survey, which is part of the

AHSQC patient-reported outcomes, at baseline and postoperative day 30 ( $\pm$  15 days). The PROMIS pain intensity questionnaire is a National Institutes of Health-developed validated tool that focuses on patient-reported outcomes of pain characteristics. This survey will be completed by patients in person during enrollment, and either in person, by telephone interview or virtual visit for 30-day follow-up, if a patient is unable to come to the clinic during the defined time frame (30days $\pm$ 15days).

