propose a registry-based randomized clinical trial through the Americas Hernia Society Quality Collaborative (AHSQC). The AHSQC is a multicenter, nationwide quality improvement effort with the mission of improving the quality of hernia care [16]. We hypothesize that a TAP block with Exparel®, performed intraoperatively by a surgeon during open ventral hernia repair with mesh placed in retromuscular position, will result in decreased opioid requirements, reduced immediate and extended postoperative pain scores, shorten length of hospital stay, and improved quality of life when compared to a TAP block with Bupivacaine hydrochloride or placebo (normal saline), performed in the same manner and in the same population.

The aims of this study are:

Specific Aim #1: To determine if intra-hospital opioid requirements over initial 72 hours differ following the administration of Exparel®, Bupivacaine hydrochloride, or placebo (normal saline) through a TAP block during open ventral hernia repair with retromuscular mesh placement.

Opioid consumption will be assessed by measuring the cumulative dose of opioids administered through intravenous and oral preparations. Intravenous opioids will include all opioids infused through a patient-controlled analgesia device (PCA) and intravenously as a rescue medication for breakthrough pain. Specific time points for assessments are: at post-anesthesia care unit (PACU/POD0), and daily during the hospital stay up to a maximum of 7 days. Opioid requirements will be recorded and converted into morphine equivalents for standardization. In addition, we aim to record and analyze: (1) amount of opioids administered intraoperatively by the anesthesiologist, (2) cumulative dose of opioids during the first 7 days of hospital stay and (3) time to first oral opioid use.

Specific Aim #2: To determine if immediate and extended pain scores differ following the administration of Exparel®, Bupivacaine hydrochloride, or placebo (normal saline) through a

TAP block during open ventral hernia repair with retromuscular mesh placement. Immediate time points include while patients are at PACU/POD0, and daily during the hospital stay up to a maximum of 7 days. An extended time point includes 30-days postoperatively.

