## POWER CALCULATION

Sample size and power calculation for this study were performed by an experienced statistician. Our primary outcome of interest on this study is to determine if Exparel® is able to decrease the total amount of opioids used during the entire hospital length of stay, especially in the first 72 hours where Exparel® should be acting. We have hypothesized that when compared to placebo, Exparel® will confer a 30% decrease in total opioid consumption during hospital stay. This was defined by clinical judgment since there is a lack of published data reporting a clinically significant reduction in opioid requirements as a consequence of other interventions. Additionally, other protocols studying Exparel® have also hypothesized that the intervention would confer the same degree of opioid use reduction. Considering a 30% reduction in total opioids consumption, an alpha of 0.05, a beta of 0.20, our study will need a sample size of 49 patients per arm to achieve a statistical power of 80%. To account for losses of follow-up during the study, we have included a 10% drop-out rate in our power calculations to anticipate the latter.

Considering a 10% dropout, the total sample size for this study will be 54 patients per arm. Therefore, the total is 162 subjects.

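### The outcomes section and the power calculation name different primary outcomes, and no confirmatory contrasts, testing order or error-rate control are given for the three arms

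*Combined protocol and SAP*

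**What the plan says.** **Outcomes section (Primary outcomes of Interest).** It opens: "Primary outcomes of interest are opioid requirements and pain scores over initial 72 hours of the postoperative period". The same section records the "cumulative dose of opioids from 0 hours to 72 hours after the operation and for the total hospital length of stay", the latter capped at 7 days. VAS pain is taken at baseline, on the day of surgery and on postoperative days 1, 2 and 3, then daily while in hospital. These readings are not combined into a single 72-hour measure.

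**Introduction.** Specific Aim 1 uses the 72-hour window: "To determine if intra-hospital opioid requirements over initial 72 hours differ following the administration of Exparel®, Bupivacaine hydrochloride, or placebo (normal saline"). It lists the 7-day cumulative dose as an additional item. The study hypothesis expects Exparel to do better than both bupivacaine and placebo.

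**Power calculation.** The primary outcome is singular here: whether Exparel can "decrease the total amount of opioids used during the entire hospital length of stay, especially in the first 72 hours". The effect size follows: "We have hypothesized that when compared to placebo, Exparel® will confer a 30% decrease in total opioid consumption during hospital stay". The inputs are "Considering a 30% reduction in total opioids consumption, an alpha of 0.05, a beta of 0.20", giving 49 per arm, 54 after dropout and 162 in total. Pain and Exparel versus bupivacaine are not sized.

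**Statistical analysis.** The statistician will "determine the appropriate statistical tests for each outcome of interest". Opioids, pain, length of stay and quality of life are to be compared by Mann-Whitney tests. The pairs of arms are not named. There is no order, alpha split or adjustment, and no rule on whether one or both primary outcomes must succeed.

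**The concern.** A reader of the results needs to know which single test, or which ordered set of tests, decides the trial. Here the section that defines the outcomes gives two and the section that justifies the sample size gives one, over a different window. Three arms allow three pairwise comparisons, of which one was sized and two appear in the hypothesis.

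Two things are at stake. First, the stated alpha of 0.05 holds for the sized comparison, but nothing in the plan keeps it at 0.05 across two outcomes and several contrasts. Second, the choice of outcome, window and contrast could be made after the arms are revealed. The blinding of patients, surgeons and data abstractors does not prevent that.

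**Working it through.** **1. The plan's own figure.** For two means, n per arm = 2 × (z for alpha + z for power)² × (SD/difference)². The plan gives no mean, SD or sidedness, so 49 cannot be reproduced forwards. Backwards, assuming a two-sided test, the standardised effect is (1.960 + 0.842) × √(2/49) = 0.566 (0.572 with the t distribution). For a 30% reduction this implies SD/control mean = 0.30/0.566 = 0.53. After that, 49 × 1.10 = 53.9, rounded to 54, and 54 × 3 = 162, as stated. The calculation describes one outcome, one contrast and one undivided alpha.

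**2. The sections side by side.**

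| Section | Outcome | Window | Contrast |
|---|---|---|---|
| Primary outcomes | opioids and pain | 72 h (whole-stay opioids also recorded) | none named |
| Specific Aim 1 | opioids | 72 h | three arms listed |
| Hypothesis | opioids, pain, stay and quality of life | immediate and extended pain; no opioid window | Exparel vs bupivacaine or placebo |
| Power calculation | opioids only | whole stay, emphasis on 72 h | Exparel vs placebo |
| Statistical analysis | opioids, pain, stay, quality of life | none | none named |

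**3. False-positive rates.** Assumptions: no true effect, two-sided 0.05 per test, 49 per arm, correlation between opioids and pain from 0 to 0.7, and any significant result counted as success. As a check, two independent tests give 1 − 0.95² = 9.75%. Correlation and shared arms lower such figures, so the rates were simulated with Mann-Whitney tests (100,000 runs per setting). A normal approximation with 1,000,000 draws agrees to within about 0.3 percentage points.

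| Reading | False-positive rate |
|---|---|
| Sized comparison only | 5% |
| Both outcomes required, Exparel vs placebo | 0.3–1.5% |
| Either outcome, Exparel vs placebo | 8.4–9.7% |
| Either outcome, two Exparel contrasts | 15.0–17.1% |
| Either outcome, all three pairs | 19.8–22.7% |

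Counting only false results that favour Exparel (normal approximation), one test gives 2.5%, either outcome on one contrast 4.2–4.9%, and either outcome on the two Exparel contrasts 7.4–8.9%. That is about half the two-sided figures, with a similar relative inflation.

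**4. What a fixed order costs.** Assume an effect of 0.57 SD versus placebo on both outcomes and bupivacaine at half of it. Exparel versus bupivacaine on opioids is then significant in about 28–29% of trials. If pain is tested only after that comparison, it is reached in about 26–28% of trials, and pain versus placebo is claimed in about 20–26%. If pain versus placebo is tested second, it is claimed in about 61–72%. With bupivacaine at three-quarters of the effect, pain placed behind it is reached in about 10%.

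**5. Kruskal-Wallis gates.** Suppose placebo differs on opioids, Exparel equals bupivacaine, and pain has no effect. Opening pain after the opioid Kruskal-Wallis test alone, at full alpha, gives 7.5–9.6% error. Opening it only after all three opioid pairs are significant gives 4.7–5.1%. Splitting alpha 0.025/0.025 between the outcomes, with a gate in each, gave about 4–5% across the null settings tried.

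**The case against.** The best defence is that the plan fixes more than it seems to. The outcomes section and Aim 1 agree on 72 hours, and the power calculation itself stresses that period. Mann-Whitney tests, an alpha of 0.05 and one sized contrast are all stated. This stands: a reader might infer that nothing is fixed, and that would be wrong. It does not remove the conflict, because the 30% effect behind the sample size is for the whole stay, and pain is primary in one section and absent from the other.

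A reader might also infer that the trial's false-positive rate is 15–17%. The documents do not support that. No section says that either outcome suffices, and the hypothesis joins its outcomes with a conjunction. The hypothesis is also directional, so false claims of benefit would be about half as frequent. The figures show what the text permits, not what it prescribes.

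Finally, a reader might infer that two-group tests are wrong in a three-arm trial. Pairwise tests are valid there. The gap is that the pairs are not named or ordered.

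**Conclusion.** The point holds. Two sections contradict each other on the outcome that decides the trial, and the plan does not control the error rate beyond the one sized comparison. The false-positive rate is 5% if only that comparison counts. It is about 8–10%, 15–17% or 20–23% on progressively wider readings, and there is no inflation if both outcomes must succeed on one contrast. The inflated figures rest on a two-sided 0.05 per test, an assumed correlation of 0 to 0.7, and the any-success rule, none of which the plan states. The 80% power was stated only for whole-stay opioids, Exparel versus placebo. It does not carry over to 72-hour opioids, pain or Exparel versus bupivacaine. The matter should be settled before unblinding.

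**What to change.** Before unblinding:

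- Reconcile Aim 1, the primary outcomes section and the power calculation on one opioid window. Restate which outcome the 80% power applies to.
- Make that opioid outcome, Exparel versus placebo, the first confirmatory test at two-sided 0.05.
- Name one summary of VAS pain over 0–72 hours.
- Prespecify a procedure for any further confirmatory comparisons, such as a fixed order, or an alpha split applied once the first test is significant. The order after the first test is the sponsor's choice.
- Report all other comparisons with confidence intervals and no confirmatory claim.

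The cost is one paragraph and one corrected sentence, with no added patients for the first test. Under a fixed order, later tests cannot be claimed once an earlier one fails, so placing pain behind Exparel versus bupivacaine on opioids is expensive (step 4 of the working). If alpha is instead split between the outcomes from the start (0.025 each), power for the sized comparison at 49 per arm falls from 80% to about 71%, and 60 per arm before dropout would restore it. If Kruskal-Wallis gates are preferred, pain should not open at full alpha on the opioid gate alone; the split, or waiting for all opioid pairs, keeps the error near 5%.
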